9.5.2.1.2 Rupture or Surgical Treatment of AAA

Annual Incidence Rate of AAA Rupture, Open Surgical Treatment, Endovascular Repair

Population	:	FAS
Group	:	
• Study Arm• Product Use Category
Contents		
• Count the number of patients for the following variables
➢ Open surgical AAA treatment or AAA endovascular repair➢ AAA rupture
Definitions		
Number of patients were calculated by person-year-method: number of patients event occurred / (sum of days until event occurred / 365.25).
 
Days until event occurred is as follows:
 
 Date of decision to perform open surgical AAA treatment or AAA endovascular repair - randomization date + 1.
 
 Date of AAA rupture - randomization date + 1.
 
 For those without experiencing the event.
 
 Subject Reference End Date - randomization date + 1.

Output	:	
Annual Incidence Rate of AAA Rupture, Open Surgical Treatment, Endovascular Repair -FAS-
 
Annual Incidence Rate of AAA Rupture, Open Surgical Treatment or Endovascular Repair by Product Use Category -FAS-
 
Listing of Patients Annually Undergoing AAA Rupture, Open Surgical Treatment, Endovascular Repair

Confidentiality Statement

Data and information contained in this document are considered to constitute trade secrets and confidential commercial information, and the legal protections provided to such trade secrets and confidential information are hereby claimed under the provisions of applicable law. No part of this document may be publicly disclosed without the written consent of Philip Morris Products S.A.

9.5.2.1.3 Growth of maximum minor-axis AAA

Growth of maximum minor-axis AAA	
Population	: FAS
Group	: 
 • Study Arm • Product Use Category
Contents	
 • Count the number of patients and percentage, and 95% confidence interval for the following variables 
 ➢ Increase in Maximum minor-axis AAA diameter of more than 5 mm within 6 months ➢ Overall maximum minor-axis AAA diameter >55mm in male patients ➢ Overall maximum minor-axis AAA diameter >50mm in female patients
Sample code	
Confidence interval will be calculated based on the Clopper-Pearson exact confidence interval method.
 $P = X / N$ $P_U = \frac{\nu_1 F_{\nu_1, \nu_2}(\alpha/2)}{\nu_2 + \nu_1 F_{\nu_1, \nu_2}(\alpha/2)}, \quad \nu_1 = 2(X+1)$ $P_L = \frac{\nu_2}{\nu_2 + \nu_1 F_{\nu_1, \nu_2}(\alpha/2)}, \quad \nu_2 = 2(N-X)$ <pre>proc freq data = INPUT ; weight VAR1 / zeros ; table VAR2 / binomial alpha = 0.05 ; output out = OUTPUT binomial ; run ;</pre>
Output	: 
Summary of Growth of maximum minor-axis AAA -FAS-
 
Summary of Growth of maximum minor-axis AAA by Product Use Category -FAS-

Confidentiality Statement

Data and information contained in this document are considered to constitute trade secrets and confidential commercial information, and the legal protections provided to such trade secrets and confidential information are hereby claimed under the provisions of applicable law. No part of this document may be publicly disclosed without the written consent of Philip Morris Products S.A

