12.7 Secondary Analysis

Descriptive statistics for the maximum minor-axis AAA diameter will be summarized at each visit and overall (across all patients). The endpoints will also be summarized by strata (maximum-minor-axis AAA diameter, CC consumption, sex).

Urinary NEQ, and Total NNAL, Total NNN, and CEMA levels (concentration data adjusted for creatinine will be analyzed on a logarithmic scale) using an MMRM with the logarithmic transformation.

Descriptive statistics for the secondary endpoints shown below, will be summarized at each visit, except for vital signs (systolic and diastolic blood pressure) which will be summarized

Confidentiality Statement

Data and information contained in this document are considered to constitute trade secrets and confidential commercial information, and the legal protections provided to such trade secrets and confidential information are hereby claimed under the applicable provisions of applicable law. No part of this document may be publicly disclosed without the written consent of Philip Morris Products S.A.

every 12 months, by exposure group and overall (across all patients) in the FAS (unless otherwise defined):

- Time from diagnosis of AAA until open surgical AAA treatment or endovascular repair
- Time from diagnosis of AAA until AAA rupture
- Annual growth rate of AAA
- Nicotine equivalents (NEQ): molar sum of free nicotine, nicotine-glucuronide, free cotinine, cotinine-glucuronide, free trans-3'-hydroxycotinine, trans-3'-hydroxycotinine-glucuronide in spot urine (expressed as concentration adjusted to creatinine)
- Systolic and diastolic BP
- Body weight and waist circumference

For the secondary endpoints shown below, the number at each visit and overall (across all patients) will be described:

- Number of patients with open surgical AAA treatment or endovascular repair annually (based on date of decision to perform open surgical AAA treatment or AAA endovascular repair)
- Number of patients with a AAA rupture annually (based on date of AAA rupture)
- Number of patients with an increase in maximum minor-axis AAA diameter of more than 5 mm within 6 months
- Number of patients with an overall maximum minor-axis AAA diameter >55mm in male patients and >50mm in female patients
-
- Incidence of IQOS malfunctions and misuses
- Number of tobacco products used, (including CC and HeatSticks) based on self-reporting

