3.2 Secondary Objectives and Endpoints

The secondary objectives of this study are:

1. To describe the time from diagnosis of the AAA until open surgical AAA treatment or AAA endovascular repair or AAA rupture in patients who switch from smoking CIG to using IQOS, as compared to patients who continue smoking CIG and patients who had stopped smoking.

Endpoints (over the entire study period):

- Date of diagnosis
 - Date of decision to perform open surgical AAA treatment or AAA endovascular repair
 - Date of AAA rupture
2. To describe the number of open surgical AAA treatment or AAA endovascular repair and AAA rupture in patients who switch from smoking CIG to using IQOS, as compared to patients who continue to smoke CIG and patients who had stopped smoking.

Endpoints (number per year across all visits):

- Number of patients with open surgical AAA treatment or AAA endovascular repair annually (based on date of decision to perform open surgical AAA treatment or AAA endovascular repair)
 - Number of patients with AAA rupture annually (based on date of AAA rupture)
3. To evaluate the number of AAA growth above 5 mm in 6 months and the number of patients with an overall maximum minor-axis AAA diameter >55mm in male patients and >50mm in female patients, in patients who switch from smoking CIG to using IQOS, as compared to patients who continue smoking CIG and patients who had stopped smoking.

Endpoints (number per year across all visits):

- Number of patients with an increase in maximum minor-axis AAA diameter of more than 5 mm within 6 months
- Number of patients with an overall maximum minor-axis AAA diameter >55mm in male patients and >50mm in female patients

Confidentiality Statement

Data and information contained in this document are considered to constitute trade secrets and confidential commercial information, and the legal protections provided to such trade secrets and confidential information are hereby claimed under the provisions of applicable law. No part of this document may be publicly disclosed without the written consent of Philip Morris Products S.A

4. To monitor the safety profiles associated with IQOS use, CIG smoking and smoking cessation during the study.

Endpoints (over the entire study period):

- Incidence of Adverse events (AEs) / serious adverse events (SAEs)
- Vital signs - change from Baseline (systolic and diastolic blood pressure, pulse rate and respiratory rate)

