9.1.3 Descriptive Statistics

Data will be presented in listings, enrollment arm, patient, and study visit, unless otherwise specified.

For continuous data, summary statistics will include the number of patients with non-missing values [n], number and percent of patients with missing data, the mean and standard deviation (SD), median, first and third quartiles, minimum and maximum, and 95% confidence interval (CI). Log-normally distributed data (e.g., BoExp data) will also include the geometric mean and coefficient of variation (CV) in addition to the mean and SD. Post-baseline summaries will include change from baseline apart from log-normal variables which will present % change from baseline (see Section 5.1.2).

Confidentiality Statement

Data and information contained in this document are considered to constitute trade secrets and confidential commercial information, and the legal protections provided to such trade secrets and confidential information are hereby claimed under the provisions of applicable law. No part of this document may be publicly disclosed without the written consent of Philip Morris Products S.A.

For categorical data, frequency counts and percentages will be presented. Percentages of missing values will be computed using the number of patients [N] included in the corresponding group in the denominator, while percentages related to ‘non-missing’ categories will be computed using the number of patients with non-missing values in the denominator.

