9.1.8 Confidence Interval

All confidence intervals will be 95% CIs.

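### The two growth endpoints are defined as numbers per year, but the SAP plans only a count and a simple percentage, without year, visit or follow-up time

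*SAP*

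**What the plan says.** Secondary objective 3 has two endpoints: growth of more than 5 mm within six months, and a diameter above 55 mm in men or 50 mm in women. In both Protocol 3.2 and SAP 3.2 they stand under the heading "Endpoints (number per year across all visits").

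Protocol 12.7 says of the same endpoints that "the number at each visit and overall (across all patients) will be described".

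SAP 9.5.2.1.3 gives the instruction "Count the number of patients and percentage, and 95% confidence interval for the following variables". The estimator is P = X/N, and "Confidence interval will be calculated based on the Clopper-Pearson exact confidence interval method". The population is the FAS, and results are grouped by study arm and by product use category. The section has no year, no target visit, no follow-up time, no censoring rule and no definition of N.

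SAP 9.5.2.1.2, one section earlier, covers repair and rupture, whose endpoints carry the same per-year heading. There "Number of patients were calculated by person-year-method", that is, "number of patients event occurred / (sum of days until event occurred / 365.25").

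SAP section 7, which records departures from the protocol's analyses, does not mention the growth endpoints. SAP 9.1.5 has missing-data rules for exposure biomarkers and product use, but none for diameters.

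**The concern.** The growth endpoints are not reported in the unit in which they are defined. The by-visit counts of Protocol 12.7 are also dropped without being listed as a change.

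The omission matters because follow-up will not be equal. The investigational period lasts up to three years with a CT every six months, but patients may withdraw, and Protocol 5.2.1 requires discontinuation at repair or rupture. The early termination schedule (Protocol 9.4, Table 7) lists no CT, and SAP 9.1.6 keeps unscheduled data out of the tables. A simple proportion gives a patient seen once at six months the same weight as one scanned through to 36 months. If retention differs between groups, X/N mixes growth with retention.

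The same table is produced by product use category. SAP 5.7 sets conditions at every visit from V3 to V8 and puts all remaining cases in a residual category. Read literally, early leavers collect in that category, so follow-up would differ between these groups by construction.

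**Working it through.** The documents give no event rate, dropout rate or planned event count for these endpoints, so there is no figure of the plan's own to reproduce. What follows compares the texts and then illustrates the effect.

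**Step 1: side by side.**

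| Place | Unit or method |
|---|---|
| Protocol 3.2, SAP 3.2 | number per year, across visits |
| Protocol 12.7 | number by visit and overall |
| SAP 9.5.2.1.3 (growth) | count, X/N, Clopper-Pearson interval |
| SAP 9.5.2.1.2 (repair, rupture) | patients with event / person-years |

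**Step 2: who counts as a non-event.** N is undefined, so there are two readings.
- N is the FAS: every leaver without a recorded event is in the denominator as a non-event.
- SAP 9.1.3 applies, under which percentages of non-missing categories "will be computed using the number of patients with non-missing values in the denominator": a patient with no evaluable post-baseline scan drops out of N. A leaver with at least one evaluable scan and no event still counts as a full non-event.

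The two readings differ only for patients without an evaluable post-baseline scan.

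**Step 3: size under assumed values.** Let r be a constant yearly event rate, equal in all groups, and let a fraction d leave uniformly over three years, independently of growth.

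- Followed for three years: F = 1 − exp(−3r)
- Leaving uniformly over three years: L = 1 − F/(3r)
- Expected X/N: (1 − d)F + dL

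For r = 0.10: F = 1 − exp(−0.3) = 0.259; L = 1 − 0.259/0.3 = 0.136; with d = 0.5, 0.5 × 0.259 + 0.5 × 0.136 = 0.198.

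| Rate per year | d = 0 | d = 20% | d = 50% | Events per person-year |
|---|---|---|---|---|
| 0.05 | 13.9% | 12.6% | 10.5% | 0.05 throughout |
| 0.10 | 25.9% | 23.5% | 19.8% | 0.10 throughout |
| 0.20 | 45.1% | 41.1% | 35.0% | 0.20 throughout |

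The percentage falls as early leaving rises, while the rate stays fixed.

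**Step 4: the scale of this study.** Protocol 4.4 reports 32 patients enrolled when recruitment was stopped; numbers per arm are not given. Assume 32/3, about 11, per arm, with 2 events in each arm at 1.5 years.

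- Arm A, everyone else followed for 3 years: 2 × 1.5 + 9 × 3 = 30 person-years.
- Arm B, 5 event-free patients leave at 1 year: 2 × 1.5 + 5 × 1 + 4 × 3 = 20 person-years.
- SAP method: 2/11 = 18.2% in both arms (95% CI 2.3% to 51.8%).
- Rate: A 2/30 = 0.067 per person-year (exact Poisson 95% CI 0.008 to 0.241); B 2/20 = 0.100 (0.012 to 0.361).

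The percentage hides a 1.5-fold difference in observed rate, but the intervals are very wide by either method.

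**The case against.** **Protocol 12.7 itself plans an overall count and does not ask for person-time.** This stands. A reader might infer that the overall count is an undeclared departure, or that the per-year heading demands person-years. The documents support neither. The heading could equally mean counts by study year, and 9.5.2.1.2 supports person-years only by analogy. What is missing is any per-year or by-visit result.

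**The SAP has no rule that early leavers are event-free for the whole study.** This also stands: N is undefined, and 9.1.3 may remove patients without scans. But by Step 2 the effect remains for leavers who were scanned at least once.

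**Compulsory discontinuation at repair need not lower X/N.** A reader might infer that it does so generally. Protocol 2.1 names large diameter and rapid growth as common indicators for repair, so many such patients may already have met the endpoint, and they are counted correctly. A narrower route remains. Protocol 2.1 states the indicators as at or above the thresholds, while the endpoints require values beyond them. Protocol 7.4.9 bases the repair decision on the site's reading, while study diameters are read centrally. A patient can therefore leave for repair without a recorded growth event. Such leaving is related to disease, and person-years does not remove it.

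**Differential retention is visible elsewhere.** SAP 9.2 tabulates discontinuation with reasons, and 9.5.1.2 gives diameters at each visit. That helps a careful reader but does not supply the endpoint in its own unit. Table layouts sit in a separate shell document that is not available here.

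**Conclusion.** The mismatch is real and the consequence modest. As written, SAP 9.5.2.1.3 does not report the growth endpoints per year or by visit, leaves N open, and differs without explanation from the method used for repair and rupture.

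Unequal retention alone can move X/N. In the assumed scenarios, half of a group leaving uniformly lowers the expected percentage by 3.4 points (13.9 − 10.5) at 0.05 per year, 6.1 (25.9 − 19.8) at 0.10 and 10.1 (45.1 − 35.0) at 0.20. These figures rest on a constant rate and on leaving unrelated to growth; they illustrate the effect and do not predict this study's distortion.

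With about 32 patients the intervals will be wide, and no hypothesis is tested, so the point affects how a descriptive table is read and not a formal conclusion. It is a desirable improvement and not a critical fault.

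**What to change.** In SAP 9.5.2.1.3:

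- Add the number of patients with a first event divided by person-years under CT surveillance, with an exact Poisson 95% interval.
- Run time from V2 (randomization date for IQOS and CIG, enrollment date for SC) to the first event or the last centrally read scheduled CT. A cross-reference to 9.5.2.1.2 is not enough: that section starts every patient at a randomization date, which the SC arm lacks, ends event-free time at the subject reference end date, and specifies no interval.
- Add counts by visit or study year, with the number still under CT surveillance.
- Define N, separately for men and women for the 55 mm and 50 mm criteria.
- Keep the overall count and percentage as a secondary line.
- Show the rate beside the repair and rupture counts, because person-years corrects for unequal follow-up but not for disease-related leaving.

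The cost is a SAP wording change and a few extra table columns; no new data are needed.

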4.4 Patient recruitment

In spite of significant efforts undertaken to improve the recruitment of patients into this study, the recruitment rate remains low. Indeed, after over a year of recruitment only 32 patients were enrolled out of 114 planned. Furthermore, the forecast until June 2020 shows only 15 new patients potentially eligible to participate in the study. In addition, the recruiting sites are reaching the limits of available patients (recruitment is limited to existing patients only), and new sites joining the study have more limited pool of patients as compared to the originally selected sites. The pool of the new sites to be potentially suitable for patients recruitment has also now reached the limits - during the site selection/qualification process most promising sites were already contacted. In such a situation, it is not possible to predict the length of the recruitment needed to reach 114 patients, if at all possible. Therefore, rather than terminating the study, which would result in loss of site's and patient's efforts and lack of any new scientific knowledge for the broader community, it was decided to stop recruitment early and to continue the follow up of patients already recruited. This would still allow an evaluation of already collected data to gather evidence of the impact of switching to IQOS on the evolution of the disease in patients suffering from abdominal aortic aneurysm.

In addition, to ease the burden for the patients and to avoid potential issues with retention rate and missing data, it was also decided to decrease the number of procedures, such as those related to co-morbidities, and to shorten the duration of the follow-up from five to three years.

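### The Clopper-Pearson formula printed in SAP 9.5.2.1.3 gives only the upper limit's degrees of freedom, so its lower limit equals one minus the upper limit and disagrees with the code beside it

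*SAP*

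**What the plan says.** SAP 9.5.2.1.3 (Growth of maximum minor-axis AAA) covers the two outcomes of secondary objective 3: growth of more than 5 mm within 6 months, and a diameter above 55 mm in men or above 50 mm in women. Counts, percentages and 95% intervals are tabulated by study arm and by product use category. On the interval it says: "Confidence interval will be calculated based on the Clopper-Pearson exact confidence interval method". SAP 9.1.8 sets the level: "All confidence intervals will be 95% CIs".

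The same table cell prints, in the notation used here:

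- P_U = ν1·F / (ν2 + ν1·F)
- P_L = ν2 / (ν2 + ν1·F)

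F is the α/2 point of the F distribution on (ν1, ν2). One definition of each degree of freedom appears: ν1 = 2(X+1) on the line of P_U, and ν2 = 2(N−X) on the line of P_L.

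Sample PROC FREQ code follows, with the option "table VAR2 / binomial alpha = 0.05". It does not use the printed formula and names no event level.

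**The concern.** The exact upper and lower limits need different degrees of freedom. The upper uses 2(X+1) and 2(N−X); the lower uses 2(N−X+1) and 2X. The SAP gives only the first pair, and the two printed expressions share a denominator, so they appear to be tied together in a way that an exact interval is not.

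This is the only interval method specified for secondary objective 3. Protocol 12.1 requires the analyses to follow the SAP once it is signed. Formula and code stand in one cell with no rule on which prevails, so a programmer who works from the formula would not match one who runs the procedure.

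**Working it through.** The documents give no numerical limit to reproduce, so the check is of the formula itself.

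**Inputs.** The formula and degrees of freedom are from SAP 9.5.2.1.3. The 95% level (SAP 9.1.8) gives α/2 = 0.025, with F taken as the upper 2.5% point. Final group sizes are not given. Protocol 4.4 says only that "after over a year of recruitment only 32 patients were enrolled out of 114 planned", across three arms. The values of N below are therefore assumptions: about 8 to 16 per arm, with smaller groups possible by product use category or sex.

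**Algebra.** With one pair of degrees of freedom,

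P_L + P_U = (ν2 + ν1·F) / (ν2 + ν1·F) = 1, so P_L = 1 − P_U.

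One minus the exact upper limit for X events is the exact lower limit for N−X events. The printed P_L is therefore the lower limit for the complement, and it is right for the event only when X = N−X, that is X = N/2.

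**One case in full: N = 11, X = 1.** ν1 = 4, ν2 = 20, F = 3.5147, ν1·F = 14.059.

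- Printed P_U = 14.059 / 34.059 = 0.4128, which equals the exact upper limit.
- Printed P_L = 20 / 34.059 = 0.5872.
- Lower limit with its own degrees of freedom: ν1 = 2(11−1+1) = 22, ν2 = 2, F = 39.452, so 2 / (2 + 867.95) = 0.0023, which equals the exact lower limit.

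**Further cases.**

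| N | X | Printed P_L | Printed P_U | Exact interval | Crossed? |
|---|---|---|---|---|---|
| 5 | 0 | 0.4782 | 0.5218 | 0 to 0.5218 | no |
| 8 | 1 | 0.4735 | 0.5265 | 0.0032 to 0.5265 | no |
| 10 | 5 | 0.1871 | 0.8129 | 0.1871 to 0.8129 | no (X = N/2) |
| 11 | 0 | 0.7151 | 0.2849 | 0 to 0.2849 | yes |
| 11 | 1 | 0.5872 | 0.4128 | 0.0023 to 0.4128 | yes |
| 11 | 2 | 0.4822 | 0.5178 | 0.0228 to 0.5178 | no |
| 12 | 2 | 0.5159 | 0.4841 | 0.0209 to 0.4841 | yes |
| 16 | 2 | 0.6165 | 0.3835 | 0.0155 to 0.3835 | yes |

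**When the limits cross.** P_L exceeds P_U whenever P_U is below 0.5. That happens for X = 0 at N = 6 to 8, X ≤ 1 at N = 9 to 11, X ≤ 2 at N = 12 to 14, and X ≤ 3 at N = 15 or 16. It never happens at N ≤ 5. The table shows that uncrossed limits can still be badly wrong: at N = 8, X = 1 the printed interval is 0.474 to 0.527 around an estimate of 1/8 = 0.125.

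**Could another reading of F rescue it?** No. With the lower-tail point at N = 10, X = 0, the formula gives P_L = 0.9975 and P_U = 0.0025.

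**Code.** PROC FREQ with BINOMIAL computes exact limits without the printed formula. When no level is named it analyses the first level of the variable. If VAR2 were coded 0/1 or N/Y, that level would be the non-event. For N = 11, X = 1 the interval would then be 0.587 to 0.998 in place of 0.002 to 0.413.

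**The case against.** The strongest reply is that no reported interval need be wrong. The section names the method correctly in words, and the code beside the formula obtains exact limits without it. A lower limit above the upper would also be noticed at once. This stands. A reader might infer that the plan will report impossible intervals for secondary objective 3; the documents do not support that, because the error reaches a result only if someone programs the formula or checks against it.

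The second reply is that the defect may lie in the extraction. This is a typeset equation in a table cell, and the printed form of P_L is the correct one once its own degrees of freedom are supplied. A lost second pair would fit. The extracted text shows no gap, so an omission in the SAP fits as well. Only the original page can settle it.

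Third, a reader might infer that crossed limits are the expected outcome. Entry diameters are capped at 49 mm in men and 44 mm in women (Protocol 5.1.1), so passing 55 or 50 mm needs more than 6 mm of growth, which makes low counts plausible. But neither document gives group sizes or event rates, and in groups of 5 or fewer the limits do not cross.

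Fourth, the missing event level is not a proven error. The code is labelled as a sample, its variable names are placeholders, and the coding of VAR2 is not given. If the event sorts first, the default is right.

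Finally, the study is descriptive with no hypothesis to test (SAP 3.5.1), so no formal decision turns on these intervals.

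**Conclusion.** The point holds as a specification error. As extracted, the printed lower limit equals 1 − P_U and is wrong unless X = N/2; the printed upper limit is correct. Under the assumed group sizes of 11 to 16, the limits cross with 0 or 1 event throughout, and with 2 events from size 12 upward. In smaller groups they may not cross, but the lower limit is still generally wrong.

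Formula and code in one cell therefore disagree. The effect on reported results is nil if the code is run with the right event level and its exact limits are taken. It is large if the formula is hand-coded or used for quality control. The conclusion depends on the extracted text being complete. The event-level point is a separate and conditional risk.

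**What to change.** 1. Check the original SAP page for a second pair of degrees of freedom. If it is there, only item 3 remains.
2. Otherwise, either give ν1 = 2(N−X+1) and ν2 = 2X for P_L, with P_L = 0 when X = 0 and P_U = 1 when X = N, or delete the formula and state that the procedure's exact limits are reported. Deletion is simpler and leaves one specification.
3. Name the event category with level= in the BINOMIAL option, so that the result does not depend on how VAR2 is coded.

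The cost is about two lines of SAP text and one code option. No data, endpoint or table changes.
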